## **C4. PHQ-9 Relevance, Specificity, Sensitivity**

We will use the Patient Health Questionnaire depression scale (PHQ-9; [name], 2001) as the primary depression outcome measure in this proposal and as the core component of MBC. The PHQ-9 consists of 9 items that map directly onto the symptoms of a major depressive episode (DSM-IV TR; American Psychiatric Association, 2000), as well as 1 item pertaining to impairment. The PHQ-9 is one of the best-validated depression measures used in >1000 research studies ([name], Spitzer, Williams, & Lowe, 2010). The PHQ-9 has depressive severity cutoff scores, is sensitive to change (Löwe, [name], Herzog, & Gräfe, 2004), and is useful for weekly administration as an indicator of treatment effectiveness ([name] & Spitzer, 2002); a five-point change reflects clinically significant reduction in symptom severity ([name] & Spitzer, 2002). Three diagnostic meta-analyses and a recent review have confirmed the good sensitivity and specificity of the PHQ-9 in making a major depressive disorder diagnosis ([name], Spitzer, Williams, & Lowe, 2010). Clinicians in our pilot study appreciated the brevity of the measure; clients stated that they thought the PHQ-9 (a) was relevant, (b) would facilitate suicidality endorsement, and (c) would help them to understand their symptoms.

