## **C5. Leveraging Technology: Interfacing Tablet Data Collection with the Electronic Health Record**

NetSmart ([name] *Letter of Support*) has agreed to support the integration of the PHQ-9 into the electronic health record system and to work with our team to develop advanced features of the MBC

interface. Total score graphical displays showing session-by-session progress will be available to clinicians within the electronic health record and to clients on their personal health record via the tablet. Clinicians and clients will be able to view individual item-level information, with suicidality highlighted for careful review. Clinically significant change (5-point reduction), and lack thereof, will be flagged from session-to-session. The PHQ-9 will be available to clients on tablet kiosks in the waiting area for completion prior to session. In our pilot, clinicians indicated the importance of tablets as they: (1) felt clinician administration of the PHQ-9 was unnecessarily time-consuming, and (2) wanted to encourage clients to take ownership of symptom monitoring given the potential therapeutic benefits (Eisen, Dickey, & Sederer, 2000). Clients in our focus group unanimously requested private completion of the PHQ-9, indicating that this would promote comfort in sharing suicidality. Tablets are a cost-effective option that has been successfully used in similar protocols (Crits-Christoph et al., 2012). The technological and clinical innovations developed for this proposal present a generalizable protocol (documented in a manual) for widespread implementation given the proliferation of electronic health records. These technological enhancements will be made in both conditions during Phase I (months 0-8; see C11. Overview of Study Design).

[figure not shown]

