**Aim 1: Hypotheses:** Tailored implementation will outperform standardized in terms of (H1a) fidelity. MBC clinician fidelity was evaluated with two variables: (1) whether the PHQ-9 was recorded in the EHR, and (2) among encounters for which the PHQ-9 was recorded, whether it was discussed. Both outcomes were modeled using generalized linear mixed models with a logit link function for a binary distribution using the lme4 package. All models included random intercepts for clinicians and patients. Models for both outcomes were constructed in an identical sequence. Models comparisons in the model-building sequence described below were evaluated using the Bayesian Information Criterion (BIC); the model with the better BIC was selected for presentation. Several unconditional growth models (i.e., models with only parameters for time) were fit (i.e., linear, quadratic, log-transformed number of months). After establishing the unconditional growth model, additional fixed effects were added in the following sequence: (1) group main effect and (2) group x time interaction. Finally, new versus existing patient status was investigated as a main effect using a dummy variable for new patient status and as a patient status x group interaction.

**Aim 2: Hypotheses:** Contextual mediators will be leveraged in the tailored condition, but serve as barriers in the standardized condition. Mediation models were fit to evaluate which contextual factors (based on clinician-completed surveys, Table 5; and, clinician selection of drop-down menu reasons for MBC deviations captured in the electronic health record) mediate the impact of the implementation condition on both clinician- and client-level outcomes. The two critical effects underlying mediation were evaluated in separate models: treatment condition predicts the mediator (path *a*) and the mediator predicts the outcome (path *b*). Specifically, mediators were assessed at the conclusion of the implementation window and the mediators were used to predict PHQ9 completion in the sustainment window. The *a* path was assessed using linear mixed models with Satterthwaite degrees of freedom

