implemented using the R lmerTest package with a random intercept for clinic. The b path was assessed using generalized linear mixed models with a logit link function for a binary distribution using the lme4 package. **Aim 3 Hypotheses:** Adapted MBC protocols (i.e., tailored condition) will outperform routine weekly administration of PHQ-9s (i.e., standardized condition) with respect to clinically significant change in depression severity from intake to week 12. Depression severity was analyzed using linear mixed models with Satterthwaite degrees of freedom implemented using the R lmerTest package. Multiple imputation was used to estimate missing values across 20 datasets in which 22.8% of patients did not complete the 12-week interview. We first assessed whether there was a change in PHQ-9 between intake and week 12 in a mixed model containing patient status as a covariate and random intercepts for patient and clinic. Next, implementation group was added to the model. In addition, number of sessions, number of sessions that the PHQ-9 was recorded, and number of sessions that the PHQ-9 was discussed were added to the model. We also examined the interactions between new patient status and the focal variables. **Power calculations.** A power analysis for the multilevel models for Aim 1 was assessed with Monte Carlo studies in which power is the proportion of significant effects (2-tailed  $\alpha$ ,  $p < .05$ ) for parameters of interest observed over repeated analyses of simulated data (Muthén & Muthén, 2002; Thoemmes, Reiser, & MacKinnon, 2010) using MPlus (version 7). For each model, 10,000 data sets were simulated and analyzed. Data in the Monte Carlo studies were simulated with the goal of identifying the smallest detectable effect size with power  $> 80$ . Dropout was simulated to reflect an increase of 5% missing data per wave. Repeated measurements were nested within participants (ICC = .50) and participants were nested in sites (ICC = .05). Average effect sizes for Aim 1 analyses were computed using an approximation of Cohen's  $d$  for growth models (Feingold, 2009). Using this metric, we are sufficiently powered to detect effect sizes as small as  $d = .46$  for the clinician models ( $N = 150$ ) and effect sizes as small as  $d = .30$  for the client models ( $N = 500$ ). For Aim 2, we conducted power analyses for the hypothesized mediation effects with the same assumptions described above but with the use of effective samples size estimates (an ICC corrected sample size) based on a design effect adjustment (Bickel, 2007) in order to use standard effect size metrics. The  $\kappa^2$  effect size for mediation (.01, .09, and .25 represent small, medium, and large  $\kappa^2$  respectively) was computed (Preacher & Kelly, 2011). We are sufficiently powered to detect effect sizes as small as  $\kappa^2 = .16$  for the clinician models and effect sizes as small as  $\kappa^2 = .10$  for the client models. For Aim 3 analyses, we are sufficiently powered to detect effect sizes as small as  $r = .27$  for clinicians and as small as  $r = .21$  for clients. The planned sample sizes are consistently sufficient for detecting medium effect sizes for clinician outcomes and small effect sizes for client outcomes, with the power to treat site as a random effect based 6 sites per condition (Atkins & Baldwin, 2013).

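### H3 is worded as clinically significant change, but Aim 3 models only continuous PHQ-9, so the difference in the proportion of clients reaching that change is neither estimated nor tested

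*Combined protocol and SAP*

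**What the plan says.** H3 is stated twice with the same endpoint, in section A (Specific Aims) and in C13a under Aim 3. The tailored condition is expected to outperform the standardized one "with respect to clinically significant change in depression severity from intake to week 12". Section A classes Aims 2 and 3 as secondary and exploratory.

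Two sections give the term a number. C4 says of the PHQ-9 that "a five-point change reflects clinically significant reduction in symptom severity". C5 describes the display in the health record: "Clinically significant change (5-point reduction), and lack thereof, will be flagged from session-to-session".

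The Aim 3 analysis in C13a reads "Depression severity was analyzed using linear mixed models with Satterthwaite degrees of freedom". It proceeds in steps: "We first assessed whether there was a change in PHQ-9 between intake and week 12 in a mixed model", then "Next, implementation group was added to the model". Counts of sessions, of sessions with a recorded PHQ-9 and of sessions with a discussed PHQ-9 follow, together with interactions with new-patient status. Missing values are multiply imputed in 20 data sets; the text reports that 22.8% of patients missed the 12-week interview.

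**The concern.** A hypothesis about clinically significant change concerns how many clients improve by a meaningful amount. A linear model of PHQ-9 concerns the average score. Unless something in the plan connects the two, a significant group effect could be reported as confirming H3 although nobody has counted the clients in each condition who reached the threshold.

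What is at stake is the wording of the Aim 3 conclusion. Readers who see the phrase in the hypothesis and a p-value beneath it would take it that the trial had shown more clinically significant improvement under tailoring.

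**Working it through.** **1. Is the term given a meaning?** Yes, but only outside the analysis plan. C4 and C5 both use 5 PHQ-9 points, and C5 makes clear that this is a reduction in one client's score. Neither H3 nor C13a repeats the figure. The reference list contains a paper on a statistical approach to clinical significance, but no section shown applies it. Five points is thus the only operational meaning available.

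**2. Does any planned model use it?** The binary models in C13a are these:

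- Aim 1: "Both outcomes were modeled using generalized linear mixed models with a logit link function for a binary distribution using the lme4 package". The two outcomes are PHQ-9 recording and PHQ-9 discussion.
- Aim 2: "The b path was assessed using generalized linear mixed models with a logit link function for a binary distribution". The outcome is PHQ-9 completion during sustainment.
- Aim 3: none.

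No model has a 5-point response as its outcome, and no rule relates the Aim 3 estimate to that threshold. The Aim 3 power statement is a correlation (r = .21 for clients), not a difference in response rates.

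**3. Is the wording merely loose?** Section A words H1b as a reduction in depression severity, which a linear PHQ-9 model addresses directly. H3 uses a different term, so it has content of its own that this model does not address.

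**4. Can the indicator be derived?** C12b and Section VII provide a PHQ-9 at baseline and at week 12 in both conditions. The entry threshold is given as above 9 or as 9 and higher, depending on the section; either way, every client can fall by 5 points.

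**5. The plan's own Aim 3 figure.** C13a gives no formula for r = .21. Assume a Fisher z test, two-sided alpha .05, 80% power, 12 equal sites and ICC .05:

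- 625 clients: design effect 1 + (625/12 − 1) × .05 = 3.554; effective n = 625/3.554 = 175.8; r = tanh(2.802/√172.8) = .210, which matches.
- 500 clients: design effect 3.033; effective n = 164.8; r = tanh(2.802/√161.8) = .217.

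**6. What would a responder comparison cost in power?** The documents give no SD of PHQ-9 change and no response rates, so this is an illustration. Read r = .21 as a balanced two-group contrast (an assumption): d = 2(.21)/√(1 − .21²) = .43. Take effective n 164.8, that is 82.4 per condition, and normal change scores with equal SDs.

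- Mean: d√(164.8/4) = 2.76; power = Φ(2.76 − 1.96) = 79%.
- Proportion falling by at least 5 points, with assumed SD 6 and mean change 3 in the standardized condition: p₀ = 1 − Φ(2/6) = .369 and p₁ = 1 − Φ(2/6 − .43) = .538, a difference of .169. SE = √[(.369 × .631 + .538 × .462)/82.4] = .0764; power = Φ(.169/.0764 − 1.96) = 60%.
- Over assumed SDs of 5 to 7 and mean changes of 2 to 5, the difference is 16 to 17 percentage points and power is 58 to 60%.

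The smallest difference detectable with 80% power solves p₁ − p₀ = [1.96√(2p̄q̄) + .84√(p₀q₀ + p₁q₁)]/√82.4. For p₀ of .30 to .50 it is 21 to 22 percentage points.

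**The case against.** The strongest reply is that a mean shift and a responder shift go together. With roughly normal change scores and equal SDs, a lower mean in one condition implies more clients past any threshold, as step 6 shows. This stands: a significant mean difference is evidence in H3's direction. It does not give the size of the responder difference or an interval for it, and the link rests on distributional assumptions that the plan does not set out to check.

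Three further points stand in whole or in part. Aim 3 is exploratory, and the co-primary client hypothesis, H1b, is worded in a way that suits a continuous outcome, so no primary claim is affected. The 5-point figure comes from the measure description and the record display, so applying it to H3 is an inference, although it is the only threshold offered. And the Aim 3 text is in the past tense and reports an observed rate of missing interviews, so anything added after that point is post hoc.

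A reader might infer something stronger: that the trial could declare success on a difference far below its own clinical threshold. The documents do not support that. Five points is a within-client change, and H3 does not require the conditions to differ by 5 points on average. The d = .30 in C13a, which might be used for such a comparison, belongs to the Aim 1 client models; Aim 3 has its own figure, r = .21. Converting either to PHQ-9 points would also need an SD that the documents do not give.

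**Conclusion.** The mismatch is real and modest. H3 as worded is not directly tested: the between-condition difference in the proportion of clients with a 5-point reduction by week 12 is neither estimated nor tested. A significant mean difference would be indirect support only. It would be wrong to infer that such a result says nothing about H3, or that the linear model is unsuitable.

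This conclusion comes from comparing the sections and depends on no assumed number beyond taking 5 points as the meaning of the term. The power figures in step 6 rest on assumed SDs, mean changes, normality, an approximate treatment of clustering and a particular reading of r = .21. They serve only to show that the responder comparison is the weaker test.

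**What to change.** 1. Keep the continuous PHQ-9 model as the main Aim 3 analysis and state its conclusion as mean PHQ-9 change.
2. Add a supportive analysis. In each of the 20 imputed data sets, derive a per-client indicator of a PHQ-9 reduction of at least 5 points from baseline to week 12. Compare it by condition in a mixed logistic model that accounts for clinic and clinician clustering. Combine across imputations and report the difference in proportions with a confidence interval.
3. State in C13a that 5 points is the threshold used for H3, citing C4.
4. Label the analysis post hoc if it is specified after data were seen.
5. Claim clinically significant change only as far as this estimate and its interval support it. Do not read a non-significant result as refuting H3.

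The cost is one additional model on data already collected and imputed. The drawback is lower power than the continuous model, so the interval may well be too wide to settle H3 either way. If the sponsor prefers not to add the model, the minimum correction is to confine the Aim 3 conclusion to mean PHQ-9 change.

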Phase 1: Pre-Implementation (Months 0-8). The PHQ-9 and fidelity measures will be embedded in the EHR and the PHQ-9 linked to tablet computers for client completion to promote feasibility. Phase 2: Randomized Implementation Trial: Dynamic Waitlist Control (Months 8-38; Sites:  $N=12$ ; Clinicians:  $N=150$ ; Clients:  $N=500$ ; mixed within- & between-subjects design). MBC implementation will occur across 4 cohorts (2-4 sites) at early and later stages (each with 5-months active implementation, 10-months sustainment) to reduce confounds (timing) and increase feasibility (phased training). Both conditions will enact the 5 strategies within the active implementation period. We will use rapid ethnography (month 1) to synthesize the needs assessment data and develop the tailored content. Phase 3: Characterization of MBC Fidelity (Months 38-48). MBC fidelity will be coded, clinician and client fidelity reports will be triangulated, and sustainment will be evaluated.

**Specific Aims.** The hybrid design yields one co-primary aim (outcomes at the clinician- and client-levels) and two secondary exploratory aims in the context of a pragmatic trial (Thorpe et al., 2009).

**Aim 1:** To compare the effect of standardized versus tailored MBC implementation on clinician-level (**1a**) and client-level (**1b**) outcomes. We hypothesize that tailored implementation will outperform standardized in terms of (**H1a**) MBC fidelity, and (**H1b**) reducing client depression severity.

**Aim 2:** To identify contextual mediators of MBC fidelity. We hypothesize (**H2**) that contextual mediators (structure, norms, etc.) will be leveraged in the tailored condition, but serve as barriers in the standardized condition.

**Aim 3:** To explore the impact of MBC fidelity on client outcomes (Chambers et al. 2013). We hypothesize (**H3**) that adapted MBC protocols (tailored condition) will outperform weekly administration of PHQ-9s (standardized condition) with respect to clinically significant change in depression severity from intake to week 12.

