#### **C14. Potential Problems & Alternative Strategies.**

Our hypothesis is that tailored implementation will outperform the standardized approach. However, it is possible that this hypothesis will not be supported. Findings of this nature would not be undesirable, but rather would illustrate that while emerging research suggests the need to contextualize implementation interventions (Fixsen, 2005; Wallerstein & Duran, 2010), this customization compromises ultimate outcomes—a critical realization for the field of implementation science. Furthermore, if we are unable to detect mediators of implementation and effectiveness outcomes included in this proposal, it may suggest the need to re-evaluate the *Framework of Dissemination*. Specifically, putative mediators of the dissemination and implementation process not included in this model might require empirical investigation. Our qualitative analyses will allow for careful examination of unanticipated mediators. At the level of the clinician, we anticipate substantial variability in competency and general approach to psychotherapy. However, we are not concerned about the effects of this variability on study outcomes because (1) randomization should result in equivalent variability across conditions and (2) MBC is conceptualized as transtheoretically relevant, regardless of the therapist’s orientation or training.

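### The Aim 3 depression model has no clinician level, so standard errors for the exploratory fidelity counts are likely modestly too small; the condition contrast is essentially unaffected.

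*Combined protocol and SAP*

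**What the plan says.** Under Aim 3, section C13a describes a linear mixed model for PHQ-9 at intake and week 12 with patient status as a covariate and "random intercepts for patient and clinic". Implementation group is added next. After that, the number of sessions, "number of sessions that the PHQ-9 was recorded, and number of sessions that the PHQ-9 was discussed were added to the model". No clinician term appears at any step, and the text does not say whether the counts enter as main effects or by time.

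Under Aim 1, the same section states: "All models included random intercepts for clinicians and patients". So the clinician identifier is available and is used in the fidelity models.

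Section A words Aim 3 as "To explore the impact of MBC fidelity on client outcomes", but the hypothesis attached to it (H3) is that tailored sites will do better than standardized sites on clinically significant change. Section A calls Aims 2 and 3 secondary and exploratory.

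Section V.C (Number of Subjects) plans an average of 42 clients per site and 3 per clinician. The power paragraph in C13a lists an ICC of .50 for repeated measures within participant and .05 for participants within site. It gives none for clients within clinician. Section C14 says: "At the level of the clinician, we anticipate substantial variability in competency and general approach to psychotherapy". It then sets this aside because randomization should balance it across conditions and because MBC applies whatever the therapist's orientation.

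**The concern.** Clients of one clinician share that clinician's skill and habits. If their PHQ-9 scores are correlated beyond what the clinic explains, a model without clinicians treats them as more independent than they are. This matters for any predictor that itself clusters by clinician.

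The fidelity counts plausibly do. Section VII has the client hand a paper PHQ-9 to the clinician, who enters it in the record, and describes that entry as optional for the clinician. Discussion of scores is also clinician behaviour. In the pilot (C9), 67% of participating clinicians used MBC at all, and clinicians' prior intention to use it correlated .67 with how often they administered the PHQ-9.

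Neither reason in C14 answers this. Randomization protects the condition contrast, but the fidelity counts are not randomized. That MBC suits every orientation does not make one clinician's clients independent. At stake is whether an association between fidelity and depression outcome is reported with an interval that is too narrow.

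**Working it through.** **The plan's own figures.** C13a gives smallest detectable correlations for Aim 3 of .27 (clinicians) and .21 (clients). Both reproduce from a design effect for site alone, at 80% power and two-sided 5%, with the recruited numbers:

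- DE = 1 + (N/12 − 1) × .05; n_eff = N/DE; r = tanh[(1.960 + 0.842)/√(n_eff − 3)].
- N = 625: DE = 3.554, n_eff = 175.8, r = .210.
- N = 187: DE = 1.729, n_eff = 108.1, r = .267.
- With the analysis targets, r = .217 (N = 500) and .284 (N = 150).

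So the stated figures are what one obtains with no clinician level among the planning inputs.

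**Inputs for the check.** Clients per clinician: m = 500/150 = 3.33 (625/187 = 3.34). Two quantities are assumptions, because the documents give neither: ρc, the ICC of PHQ-9 by clinician beyond clinic, and ρx, the share of the predictor's variance that lies between clinicians.

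**Formulas.** DE = 1 + (m − 1) × ρc × ρx. True SE / model SE = √DE. Type I error = 2 × [1 − Φ(1.96/√DE)].

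| ρc | ρx | DE | True SE / model SE | Type I error |
|---|---|---|---|---|
| .02 | .5 | 1.023 | 1.01 | 5.3% |
| .02 | 1 | 1.047 | 1.02 | 5.5% |
| .05 | .5 | 1.058 | 1.03 | 5.7% |
| .05 | 1 | 1.117 | 1.06 | 6.4% |
| .10 | .5 | 1.117 | 1.06 | 6.4% |
| .10 | 1 | 1.233 | 1.11 | 7.8% |
| .15 | .5 | 1.175 | 1.08 | 7.1% |
| .15 | 1 | 1.350 | 1.16 | 9.2% |

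Uneven caseloads act like a larger m. For illustration, m = 6 with ρc = .10 and ρx = 1 gives DE = 1 + 5 × .10 = 1.50, a true SE 22% larger, and type I error of 11.0%.

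**Simulation check.** A REML model with a clinic intercept only was fitted to 12 clinics × 12 clinicians × 3 or 4 clients, 6,000 runs per setting.

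| ρc | ρx | True SE / model SE | Type I error |
|---|---|---|---|
| 0 | 1 | 1.01–1.02 | 5.4–5.5% |
| .05 | .5 | 1.03–1.04 | 6.0–6.1% |
| .05 | 1 | 1.06–1.08 | 6.5–7.2% |
| .10 | .5 | 1.07 | 6.8% |
| .10 | 1 | 1.10–1.15 | 7.6–9.1% |

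About half a point of the excess over 5% is present even with no clinician variance, so not all of it comes from the omitted level. The ratio for the site-level group effect stayed at 0.98 to 1.03 throughout. With ρx = 0 the standard error was not too small.

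**Effect on the stated sensitivity.** Adding (m − 1)ρcρx to the site design effect moves detectable r for N = 625 from .210 to between .211 and .217 (ρc .02 to .10), and for N = 500 from .217 to between .218 and .225. The planning figures barely change.

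**Main effect or change.** A clinician intercept shifts intake and week 12 equally, so it cancels from any effect on change. Suppose instead that the clinician acts only at week 12, with unit variance at each occasion and the plan's within-participant correlation of .50. The two-occasion mean has variance (1 + .50)/2 = .75 and carries ρc/4, so its clinician ICC is (ρc/4)/.75 = ρc/3. For ρc of .02 to .10, type I error for a main effect is then only about 5.1 to 5.9%. The change score has variance 2 × (1 − .50) = 1 and carries the whole of ρc, so the first table applies to it in full. A clinician intercept would not correct that case.

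**The case against.** The strongest reply is that little of importance is touched. H3 is the condition contrast, the clinic intercept serves it, and its standard error does not move. The fidelity counts are further terms in an exploratory model, with no hypothesis or decision rule of their own. This stands, and it limits the weight of the point. It does not remove it, because the counts are the only terms in the model that address the aim as Section A words it.

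The second reply is that the problem is conditional. The documents give no clinician ICC for PHQ-9; C14 expects variation in competency and approach, which is not a measured outcome ICC. This also stands. A reader might infer that fidelity associations will certainly be declared significant too often, or that the counts vary mainly between clinicians. The documents support neither. The counts are per client and are bounded by sessions attended. They depend on whether the client completes the form (C6 lists client refusal among the reasons for deviation), and they follow a guideline set by condition or site, where an intercept already exists. A ρx of 1 is therefore a ceiling, and an ICC of .15 is three times the only between-cluster ICC in the plan.

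The third reply is that a clinician intercept may miss its target. Section XII expects new clients to be enrolled before their first therapy session, so a treating clinician's effect may appear only at week 12. That is correct, and the remedy has to allow for it.

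**Conclusion.** The omission is explicit, and the direction is right for any fidelity coefficient that clusters by clinician when PHQ-9 also varies by clinician within clinic. The size is modest: a true standard error about 1 to 11% larger than reported, and type I error of about 5.3 to 7.8% instead of 5%, for an assumed outcome ICC of .02 to .10 and half to all of the predictor variance between clinicians. At an ICC of .15 the upper end is about 9%, and uneven caseloads would raise it. If either ICC is zero there is no understatement from this source.

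A reader might infer that the tailored-versus-standardized result is also compromised. It is not: that contrast varies only between sites, and its standard error is essentially unchanged. The point is confined to the exploratory, non-randomized fidelity counts.

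**What to change.** Add a random intercept for clinician to the Aim 3 client model, alongside patient and clinic. State whether the fidelity counts are tested as main effects or against change from intake to week 12. If against change, add a clinician-by-time random effect as well, since the intercept alone does not correct that test. If the model does not converge or the fit is singular, report clinician-clustered standard errors for the fidelity coefficients. Report the estimated clinician variance so that readers can judge the assumption.

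The cost is one or two variance terms, a possible singular fit with about three clients per clinician, and slightly wider intervals for the counts. No new data are needed, because the clinician identifier is already used in the Aim 1 models. If clinician variance is near zero, the results will be close to those of the present model.
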